## Data Collection Instrument 7 - Initial Complementary Exams

Current Episode Initial Complementary Exams	Key Name	Data Type	Values
White Blood Cell Count	WBC	Integer	Number x10³
Hemoglobin	НВ	Decimal	Number (g/dL)
Potassium	К	Decimal	Number (mEq/L)
Creatinine	CRE	Decimal	Number (mg/dL)
CRP	CRP	Decimal	Number (mg/L)
INR	INR	Decimal	Number (mg/L)
Lactate	LAC	Decimal	Number (mg/dL)
Date First Plain Abdominal X ray	DFXR	Date; time	dd/mm/yy hh:mm
First AXr Stand up	FXRS	Binary	Yes/No
First AXr Air-Fluid Levels	FXRAF	Binary	Yes/No
First AXr Gastric Distension	FXRGD	Binary	Yes/No
First AXr Colonic Gas	FXRCG	Binary	Yes/No
Date Computed Tomography	DCT	Date; time	dd/mm/yy hh:mm
Computed Tomography Type	CTT	List	None; Without Contrast; IV Contrast; Oral Contrast; Double Contrast
CT Report Free Fluid	CTFF	Binary	Yes/No
CT Report Disminished Bowel Enhancement	CTDBE	Binary	Yes/No
CT Report Pneumatosis	СТР	Binary	Yes/No
CT Report Portal Gas	CTPG	Binary	Yes/No
CT Report Pneumoperitoneum	CTN	Binary	Yes/No
CT Report Small Bowel Wall Thickness	CTBWT	Decimal	Number (milimeters)
CT Report Small Bowel Diameter	CTSBD	Decimal	Number (Centimeters)
CT Report Feces Sign	CTFS	Binary	Yes/No (breadcrumb sign)
CT Report Peak Sign	CTPS	Binary	Yes/No (visible caliber change)
CT Report Whirl Sign	CTWS	Binary	Yes/No
CT Report Etiological Diagnosis	CTED	Binary	Yes/No (reported)
CT Report Diagnosis	CTE	Chain	Diagnosis (ie: single adhesion, matted adhesions, Hernia, Tumor)
AAST SBO	AAST	List	I, II, III, IV, V

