## Scope

Small bowel obstruction (SBO) and its complications are frequently seen in patients admitted through the Emergency Departments of all acute care hospitals.

[figure not shown]
There is variation in the optimal use of imaging, the appropriate timing and duration of non-operative management attempts, anti-microbial therapies and the criteria for surgical management, which results in heterogeneity in approaches and outcomes across international clinical centers. The expected number of SBO cases in most clinical centers is predictable, enabling a suitable sized cohort of patients to be gathered in the snapshot audit.

This 'ESTES snapshot audit' -a prospective observational cohort study- has a dual purpose. Firstly, as an epidemiological study, it aims to uncover the burden of disease. Secondly, it aims to demonstrate current strategies employed to diagnose and treat these patients. These twin aims will serve to provide a 'snapshot' of what we are doing now, but will also be hypothesis-generating while providing a rich source of patient-level data to allow further analysis of particular clinical question.

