#### **Primary Objective**

To explore differences in patients, management and outcomes across the entire cohort to identify areas of practice variability resulting in apparent differences in outcome warranting further study. The outcomes that the study will examine are:

- Incidence of small bowel obstruction by etiology.
- Differences in clinical presentation.
- Diagnostic work-up.
- Non-operative management strategies.
- Time to surgery and outcomes.
- Complications related to disease and/or therapies within 60 post-operative days.
- Length of Emergency Department and Hospital stay.
- Re-admission within 6 months for related conditions.

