## Data Collection Instrument 8 - Current episode, course evolution

Current Episode Course Evolution	Key Name	Data Type	Values
Severity Signs	CESS	Binary	Yes/No (if one is present: Unstable hemodynamics, peritonitis, sepsis (SIRS>2), acidosis, high lactate)
Ischemia Radiologic Signs	IRS	Binary	Yes/No (if one is YES: CTFF, CTDBE, CTP, CTPG, CTN, CTBWD>3mm, mesenteric edema)
Nasogastric/nasojejunal tube Insertion	NGTI	Binary	Yes/No
Initial NGT debit	INGTD	Integer	Number (mL)
Antibiotic Prophylaxis	PXATB	Binary	Yes/No
Antibiotic Treatment (if > 1 day)	TTATB	Binary	Yes/No
Treatment Fluids (ml/first 24h)	TTFL	Decimal	Number (ºC)
Treatmet Steroids	TTST	Binary	Yes/No
Total Urinary Output	TUO	Decimal	Number
WSOC Challenge	GGF	Binary	Yes/No
Exclusion Criteria for WSOC	GGFEC	List	No/Pregnancy/Inflamatory Bowel disease/Incarcerated hernia/Previous Radiotherapy/Mechanic inflammatory ileus/Tumor or carcinomatosis/Early postoperative period<1month/allergy to GGF)
Date WSOC	GGFD	Date; time	dd/mm/yy hh:mm
Post WSOC Vomiting	GGFPV	Binary	Yes/No
Post WSOC NGT debit	GGFNG	Decimal	Number (ºC)
Total Number of simple Abdominal X Ray	NXR	Integer	Number
Date Last Simple Abdominal X Ray	DLXR	Date; time	dd/mm/yy hh:mm
Last AX Ray WSOC in Stomach	LXR GGFS	Binary	Yes/No
Last AX Ray Deterioration	LXRD	Binary	Yes/No
Last AX Ray Colonic Air	LXRCA	Binary	Yes/No
Last AX Ray Colonic WSOC	LXRGGFC	Binary	Yes/No
Gas Pass	GP	Binary	Yes/No
Date Gas Pass	DGP	Date; time	dd/mm/yy hh:mm
Stools Pass	SP	Binary	Yes/No
Date Pass Stools	DSP	Date; time	dd/mm/yy hh:mm
Date Start Oral Feeding	DSOF	Date; time	dd/mm/yy hh:mm
Date Discharge from Emergency	DDE	Date; time	dd/mm/yy hh:mm
Emergency Department Lenght of Stay	EDLOS	Integer	Hours (calculation DDE-DOA)
Non-operative Treatment Success	COTS	Binary	Yes/No

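### Diagnostic work-up is a listed outcome, but the forms have no field for ultrasound, MRI or other imaging, so use of these cannot be reported

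*Protocol*

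**What the plan says.** The Scope section of the protocol opens its rationale with imaging: "There is variation in the optimal use of imaging". It then states the second of the audit's two purposes: "it aims to demonstrate current strategies employed to diagnose and treat these patients". The Primary Objective is to find practice variability across the cohort, and its list of outcomes includes "Diagnostic work-up" without limiting it to particular tests.

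Imaging is collected in two places:

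- **Data Collection Instrument 7** (initial exams) has "Date First Plain Abdominal X ray" with four findings from that film. It also has "Date Computed Tomography", a CT type field with the values "None; Without Contrast; IV Contrast; Oral Contrast; Double Contrast", and a series of CT report findings.
- **Data Collection Instrument 8** (course) has "Total Number of simple Abdominal X Ray", the date and findings of the last film, and the WSOC challenge with its date and whether contrast was seen in the stomach or colon.

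The Definitions section treats the WSOC challenge as both a diagnostic test and a treatment, so it belongs among the recorded examinations.

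**The concern.** An audit that sets out to describe differences in diagnostic practice needs its forms to show which tests were done. If a modality has no field, its use drops out of the data altogether, and no later statistical analysis plan can recover it.

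Two things are at stake. First, the description of work-up is incomplete for any centre that uses ultrasound or MRI, and differences in modality between centres are the kind of variability the Primary Objective looks for. Second, among patients without CT, two different groups look the same in the database: those imaged by another modality and those with nothing beyond plain film.

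**Working it through.** No sample size, power or rate in the protocol bears on this point, so the check is a reading of the forms.

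**Step 1: count fields by modality over Data Collection Instruments 1 to 10.**

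| Modality | Recorded? | Where |
|---|---|---|
| Plain abdominal film | yes | Instruments 7 and 8 |
| CT | yes | Instrument 7 |
| WSOC challenge | yes | Instrument 8, contrast position read on plain film |
| Ultrasound | no field | none |
| MRI | no field | none |
| Other imaging | no field | none |

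Neither ultrasound nor MRI is named in the body text. The derived variable for radiological signs of ischaemia in Instrument 8 is built from CT fields plus mesenteric oedema, so it names no ultrasound or MRI source either.

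**Step 2: compare two patients under these forms.** Patient A has a plain film and then ultrasound or MRI, without CT. Patient B has a plain film and nothing else. Both have a plain-film date, no CT date and CT type *None*. WSOC fields are filled according to whether that challenge was done and do not depend on other imaging. No recorded field shows which of the two had the further examination.

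**Step 3: ask what the stored values assert.** *None* is a value of the CT type field only, and for both patients it is true. No field states that no further imaging took place. The database is silent on other modalities; it does not hold a wrong value.

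**Step 4: size.** Let *t* be the share of all patients with no imaging beyond plain film, and *u* the share with ultrasound or MRI instead of CT. The group without CT then has share *t* + *u*, and the fraction of that group who did have other imaging is *u*/(*t* + *u*). The protocol gives neither input. The values below are assumptions, chosen only to show how the fraction behaves:

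- *t* = 10%, *u* = 0%: group 10%, fraction 0/10 = 0%
- *t* = 10%, *u* = 3%: group 13%, fraction 3/13 = 23%
- *t* = 10%, *u* = 10%: group 20%, fraction 10/20 = 50%
- *t* = 5%, *u* = 10%: group 15%, fraction 10/15 = 67%

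The fraction depends entirely on inputs that the documents do not supply, and it vanishes as *u* approaches zero. It is not an estimate for this cohort. The forms as designed also could not show afterwards which of these cases applied.

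**The case against.** The best defence is that the forms were kept short on purpose. The Data completion section says the instruments are meant to cover parameters in common use, and the section on missing data excludes centres with more than 5% missing in mandatory fields, which is a reason not to add items. Work-up is not defined as every possible test, and the one imaging-related research question, on WSOC use and its indications, is covered. This has weight and explains why the point is minor. It does not remove it: the statement about common parameters does not narrow the outcome listed under the Primary Objective, and Instrument 7 already goes into such detail as the whirl sign, portal gas and whether the film was taken standing.

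Three stronger readings should be resisted.

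- A reader might infer that patients imaged by ultrasound or MRI are stored as having had no further imaging, and so are misclassified. They are not. CT type *None* is correct for them, and a patient who has ultrasound followed by CT is recorded with the CT.
- A reader might infer that the audit will overstate under-investigation. That would follow only if an analyst reported absence of CT as absence of further imaging. The protocol defines no such measure.
- A reader might take the list beginning "No/Pregnancy/Inflamatory Bowel disease/Incarcerated hernia" as evidence that the cohort contains many patients imaged by other means. That list gives reasons for not using WSOC. It says nothing about which imaging these patients receive.

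**Conclusion.** The point holds as a gap in data capture. Diagnostic work-up is an outcome and imaging variation a motive, yet the use of ultrasound, MRI or other imaging cannot be reported. Patients imaged that way instead of by CT cannot be separated from patients with no imaging beyond plain film. It does not hold as a claim of wrong data or of bias in a stated estimate.

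The size is unknown and may be small, because the documents give no share of patients imaged by these modalities. The conclusion about the gap needs no assumption, since it rests only on the field lists; any percentage attached to it would be assumed. This is a modest improvement and does not threaten the audit's other outcomes.

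**What to change.** Add one multi-select item to Data Collection Instrument 7: other imaging before the treatment decision, with the values none / ultrasound / MRI / other, and a date and time for each modality ticked. The explicit *none* value separates not done from not entered. Show the date only when a modality is ticked, so that it does not count against the completeness threshold. Report work-up as combinations of modalities, and describe a patient as having no imaging beyond plain film only when CT type is *None* and the new item is *none*.

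The cost is a minor extra entry burden; sites already need the CT report to complete Instrument 7.

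If the form can no longer change, limit the imaging part of the work-up outcome to plain film, CT and WSOC. State that other modalities were not collected, and report patients without CT as exactly that, not as patients without further imaging. This costs nothing in data entry but gives up any description of ultrasound and MRI use.

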## Data Collection Instrument 8 - Current episode, course evolution

Current Episode Course Evolution	Key Name	Data Type	Values
Severity Signs	CESS	Binary	Yes/No (if one is present: Unstable hemodynamics, peritonitis, sepsis (SIRS>2), acidosis, high lactate)
Ischemia Radiologic Signs	IRS	Binary	Yes/No (if one is YES: CTFF, CTDBE, CTP, CTPG, CTN, CTBWD>3mm, mesenteric edema)
Nasogastric/nasojejunal tube Insertion	NGTI	Binary	Yes/No
Initial NGT debit	INGTD	Integer	Number (mL)
Antibiotic Prophylaxis	PXATB	Binary	Yes/No
Antibiotic Treatment (if > 1 day)	TTATB	Binary	Yes/No
Treatment Fluids (ml/first 24h)	TTFL	Decimal	Number (ºC)
Treatmet Steroids	TTST	Binary	Yes/No
Total Urinary Output	TUO	Decimal	Number
WSOC Challenge	GGF	Binary	Yes/No
Exclusion Criteria for WSOC	GGFEC	List	No/Pregnancy/Inflamatory Bowel disease/Incarcerated hernia/Previous Radiotherapy/Mechanic inflammatory ileus/Tumor or carcinomatosis/Early postoperative period<1month/allergy to GGF)
Date WSOC	GGFD	Date; time	dd/mm/yy hh:mm
Post WSOC Vomiting	GGFPV	Binary	Yes/No
Post WSOC NGT debit	GGFNG	Decimal	Number (ºC)
Total Number of simple Abdominal X Ray	NXR	Integer	Number
Date Last Simple Abdominal X Ray	DLXR	Date; time	dd/mm/yy hh:mm
Last AX Ray WSOC in Stomach	LXR GGFS	Binary	Yes/No
Last AX Ray Deterioration	LXRD	Binary	Yes/No
Last AX Ray Colonic Air	LXRCA	Binary	Yes/No
Last AX Ray Colonic WSOC	LXRGGFC	Binary	Yes/No
Gas Pass	GP	Binary	Yes/No
Date Gas Pass	DGP	Date; time	dd/mm/yy hh:mm
Stools Pass	SP	Binary	Yes/No
Date Pass Stools	DSP	Date; time	dd/mm/yy hh:mm
Date Start Oral Feeding	DSOF	Date; time	dd/mm/yy hh:mm
Date Discharge from Emergency	DDE	Date; time	dd/mm/yy hh:mm
Emergency Department Lenght of Stay	EDLOS	Integer	Hours (calculation DDE-DOA)
Non-operative Treatment Success	COTS	Binary	Yes/No

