### **Definitions**

**Mechanical small bowel obstruction (SBO):** An intrinsic, extrinsic or endoluminal process which narrows or occludes the bowel lumen and delays the passage of luminal contents.

**Ileus:** Functional motility disorder characterized by adynamic paralytic bowel, leading to many of the same symptoms of mechanical obstruction, but without a single site of obstruction demonstrable on imaging. Common causes include recent abdominal surgery, medications such as opiates, and electrolyte disturbances.

**Complete SBO:** Obstruction with no passage of luminal contents beyond the point of obstruction (Appendix A).

**Partial SBO:** Incomplete obstruction with luminal narrowing but some contents continue to pass through the intestine. This is distinguished from complete obstruction by the continued passage of bowel movements and flatus, and a non-peritonitic abdominal exam^3.

**Small bowel dilatation:** Luminal diameter of >3 cm.

**Transition zone:** Short segment area between dilated proximal bowel and decompressed distal bowel. Sometimes called a transition point and is radiographic evidence of SBO.

**Bowel compromise:** when there is ischemia or injury that has led to necrosis and/or perforation of the bowel wall.

**Adhesions:** Fibrous tissue that connects surfaces or organs within the peritoneal cavity that are normally separated. Such adhesions are the results of an adaptive healing response of the peritoneum upon tissue handling or contact with blood or purulence, but also caused by other conditions like radiotherapy, endometriosis, inflammation or local response to tumors.

**Virgin abdomen:** abdomen of a patient without prior surgery. Although there is no consensus in the literature about radiotherapy, known peritoneal inflammatory disease or primary abdominal wall hernias, in our study we will consider only those non-operated inside the definition.

Water Soluble Oral Contrast (WSOC) challenge: a combined diagnostic study and therapeutic intervention utilized in the evaluation and management of small bowel obstruction.

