#### Missing data and retrospective patient entry

The online database has been designed to allow sites to securely access an individual patient's data throughout the study period. This means that any missing or erroneous data can be altered by the local investigators whilst the data collection period is ongoing. In order to maximize data completion and emphasize its importance to collaborators, participating Centers with >5% missing data in mandatory fields (i.e. less than 95% data completeness) will be excluded from the study.

The study design means that sites may retrospectively identify eligible patients that were missed primarily and for whom contemporaneous patient and operation data was not entered.

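### The radiologic ischemia flag (IRS) in DCI 8 cannot be applied or checked as written: one of its keys is undefined, one of its signs has no field, and there is no value for patients without CT

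*Protocol*

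**What the plan says.** DCI 8 (Current episode, course evolution) defines Ischemia Radiologic Signs, key IRS, as a binary item: "Yes/No (if one is YES: CTFF, CTDBE, CTP, CTPG, CTN, CTBWD>3mm, mesenteric edema". One positive component is enough. The two components at issue are the last two, "CTBWD>3mm, mesenteric edema".

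The CT findings themselves are stored in DCI 7 (Initial Complementary Exams). Two of its fields are measurements: "CT Report Small Bowel Wall Thickness", key CTBWT, in millimetres, and "CT Report Small Bowel Diameter", key CTSBD, in centimetres. The sign "CT Report Disminished Bowel Enhancement", key CTDBE, is Yes/No. CT type, key CTT, takes the values "None; Without Contrast; IV Contrast; Oral Contrast; Double Contrast".

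The Definitions section gives small bowel dilatation as "Luminal diameter of >3 cm".

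The section on missing data and retrospective patient entry states that "participating Centers with >5% missing data in mandatory fields (i.e. less than 95% data completeness) will be excluded from the study". It does not list the mandatory fields.

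**The concern.** A composite flag is only as good as the fields it points to. IRS points to one key that the data dictionary does not contain and to one sign that no form records. It offers only Yes or No for a finding that needs a CT, while the CT type field expressly allows for patients who had none.

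IRS also does not appear to be computed by the database. The protocol labels its derived items as such: length of stay in DCI 2, time from last surgery in DCI 4, emergency department stay in DCI 8 and time to surgery in DCI 9. IRS carries no such label, so it appears to be judged and typed in locally. Under Data completion, DCI 8 may be filled in by any qualified team member, whereas DCI 7 requires an admitting staff surgeon. The person applying the rule need not be the one who recorded the CT.

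The primary objective is to find practice variability that goes with differences in outcome. If centres settle the unclear parts of IRS differently, or differ in how often they scan, their IRS rates can differ for reasons unrelated to their patients. An entry of IRS = Yes with every stored CT sign negative could be mesenteric edema or an entry error, and nothing in the database separates the two.

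**Working it through.** The protocol gives no figure for IRS to reproduce, so the check sets the two instruments side by side.

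**Step 1: match each IRS component (DCI 8) to a stored field.**

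| IRS component | Field in DCI 7 | Match |
|---|---|---|
| CTFF (free fluid) | CTFF, Yes/No | yes |
| CTDBE (reduced enhancement) | CTDBE, Yes/No | yes |
| CTP (pneumatosis) | CTP, Yes/No | yes |
| CTPG (portal gas) | CTPG, Yes/No | yes |
| CTN (pneumoperitoneum) | CTN, Yes/No | yes |
| CTBWD >3 mm | none; nearest are CTBWT (mm) and CTSBD (cm) | no |
| mesenteric edema | none in DCI 7 or any other instrument | no |

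Result: 5 of 7 components map to a stored field. IRS cannot be fully rebuilt or audited from the database.

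**Step 2: which field could CTBWD mean?** The letters BW and the unit mm both fit CTBWT. The letter D could suggest diameter, but that key is CTSBD and is recorded in cm. The protocol's own dilatation threshold is 3 cm = 30 mm, and 30 / 3 = 10. A 3 mm diameter criterion would thus sit at one tenth of the dilatation threshold and would be met by every patient with dilated bowel. That makes diameter an implausible reading and wall thickness the likely one. The document does not settle it in words.

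**Step 3: apply the rule to each CT type.**

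- CTT = None: no CT component can be positive, so the literal rule yields No. A site might instead leave the item blank. The document gives no instruction. If IRS is a mandatory field, which is not stated, the 95% completeness rule would favour No over a blank.
- CT without IV contrast: only CTDBE is affected. Free fluid, pneumatosis, portal gas, pneumoperitoneum, wall thickness and edema can each still make IRS Yes.
- CT with IV contrast: all listed signs can be judged.

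A No can therefore mean a negative CT or no CT at all, and the IRS item alone does not show which.

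**Step 4: illustration, by assumption only.** Let p be the prevalence of IRS if everyone were scanned, taken as equal in scanned and unscanned patients, and let u be the share unscanned and entered as No. The apparent prevalence is p(1 − u). With p = 30%:

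- u = 5%: 0.30 × 0.95 = 28.5%
- u = 20%: 0.30 × 0.80 = 24.0%

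Neither p nor u is in the documents. The example shows the direction of the effect, not its size in this study.

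**The case against.** **The key is a typing slip.** The other five CT keys in the rule match DCI 7, CTBWT is the wall-thickness field recorded in millimetres, and it is stored as a number, so an analyst can recompute that component whatever a site entered. This largely stands. A reader might infer that a diameter reading would turn IRS positive in nearly every scanned patient, but that needs a clinician to accept a 3 mm bowel diameter as a sign of ischemia against the protocol's own 3 cm definition. The slip should still be corrected, because sites see the rule, not the intention.

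**The protocol does not say that unscanned patients get No.** Correct. It follows from the literal rule and the absence of any other value, but a blank is possible. A reader might also infer that patients scanned without IV contrast are scored No. The documents do not support that, since six of the seven components do not depend on enhancement.

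**Patients without CT or without IV contrast can be identified from CTT, and restricting the analysis is a matter for the analysis plan.** This stands as a partial repair. It does not help with mesenteric edema: an analysis plan cannot recover a sign that was never stored on its own.

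**Mesenteric edema is captured within IRS if a person enters the flag by hand.** True, but what is lost is the means to verify it or to separate it from an error.

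**IRS is not central.** This stands. No objective or research question names it. Five component signs and wall thickness are stored individually, AAST grade is recorded in DCI 7, and ischemic bowel at operation is recorded in DCI 9.

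**Conclusion.** The point holds as a fault in the data dictionary. The IRS rule cites an undefined key, counts a sign that has no field, and provides no value for a patient without CT. Five of seven components can be traced to stored data. On the literal rule an unscanned patient gets the same value as one whose CT was negative.

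A reader might go further and infer that IRS rates already differ between sites, or that the study's main comparisons are distorted. The documents do not support this. Differing interpretation is a plausible consequence of the wording, not a stated fact, and IRS is a descriptive severity flag outside the listed research questions. The size of any effect cannot be given, because the protocol states neither the share of patients without CT nor the expected frequency of ischemia signs.

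The conclusion assumes that IRS is entered by hand, inferred from the missing calculation label, and that the instruments printed in the protocol match the live database. The correction is worth making because it is specific, nearly free, and makes the flag comparable across centres.

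**What to change.** 1. Replace CTBWD in the IRS rule with the DCI 7 key that is meant. The unit points to CTBWT; the sponsor should confirm.
2. Add a Yes/No field for mesenteric edema to DCI 7, or remove the sign from the rule.
3. Make IRS a calculated field built only from stored DCI 7 fields, and label it so, as is done for time to surgery.
4. Set IRS to 'not assessable' when CTT is None, and CTDBE to 'not assessable' when no IV contrast was given. In the latter case IRS is still derived from the remaining signs.
5. Report IRS among scanned patients, with the number not assessable alongside.

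Cost: a data-dictionary edit of one key, at most one added field and one extra value. It needs no new tests and no change to patient care. The small downside is a smaller denominator for IRS. For records already entered, wall thickness and CT type allow items 1 and 4 to be applied in the analysis; mesenteric edema cannot be recovered from stored fields.
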